1C	
Users standing comfort on the Rheo knee 4/Navii is improved compared to on their prescribed MPK
	
Self-Report: PEQ item 1D
 
Please rate your comfort while standing when using your prosthesis/the test prosthesis. (1=terrible, 10=excellent)
	Rating (1-10)	
Rating of comfort improved compared to prescribed MPK
 
(89% $HDI_{low} \geq 0$ $pd > 97,0\%$ $ROPE < 2,5\%$)

Exploratory/Secondary

Phase 2 (after launch)

Clarification: More subjects may be recruited after launch of the product in order to carry out a subgroup analysis, making a technology specific comparison (hydraulic & magnetorheologic MPKs compared to Rheo knee 4/Navii). Procedures will be the same as in phase I in order to be able to combine the data from all subjects in each subgroup. Therefore, subjects will be assigned to subgroups based on their prescribed MPK at the second phase of the analysis.

Data collected at phase I may be used to inform sample size needed for phase II, as researchers will be using the same procedures as in phase I.

Table 6 Phase II – Endpoints, test methods and hypotheses

#	Hypothesis	Test Methods	Endpoints	Acceptance Criteria
2A1	Users satisfaction on functioning on the Rheo knee 4/Navii in hill/ramp descent is no worse compared to hydraulic MPKs	
Self Report: Modified PEQ ambulation subscale (item 14F)
 
Please rate your ability to walk down a steep hill when using your prosthesis/the test prosthesis?
 
1=cannot, 10=No problem
	Rating (1-10)	
No worse rating compared to prescribed hydraulic MPK
 
(89% $HDI_{low} \geq 0$ $pd > 97,0\%$ $ROPE < 2,5\%$)

2A2	Users satisfaction on functioning on the Rheo knee 4/Navii in hill/ramp descent is improved compared to Rheo Knee 3	
Self Report: Modified PEQ ambulation subscale (item 14F)
 
Please rate your ability to walk down a steep hill when using your prosthesis/the test prosthesis?
 
1=cannot, 10=No problem
	Rating (1-10)	
Improved rating compared to prescribed magnetorheologic MPK
 
(89% $HDI_{low} \geq 0$ $pd > 97,0\%$ $ROPE < 2,5\%$)

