The design will be a non-randomized single group open label prospective repeated measures (ABA). Thereby, differences in efficacies of two classes of MPKs are investigated. For each hypothesis (1A1, 1A2, 1B, 1C), i , the population parameter for Rheo Knee 4/Navii, μ_{i1} is compared to the corresponding population parameter for other MPKs, μ_{i2} . For each research question i , the null and hypothesis is $H_{0i}: \mu_{i1} = \mu_{i2}$, and the alternative hypothesis is $H_{Ai}: \mu_{i1} \neq \mu_{i2}$. Hypotheses are investigated using a Bayesian regression framework. Evidence for H_{0i} or H_{1i} is collected using the posterior distribution of differences in efficacies for each hypothesis. Using the posterior distribution, statistical measures as the 89% high density interval (HDI), the percentage in the region of practical equivalence (% ROPE), and the probability of direction (PD) will be used to gather evidence for or against each hypothesis.

Acceptance criteria relate to the 89% HDI. An 89% HDI not covering 0 indicates a true difference between the two groups.

For trial phase II, a similar procedure will be performed and uses adjusted priors for model generation. These priors will be generated from the posterior distribution of the first trial, therefore making the prior more informative.

Using bayes theorem, the distribution of differences for each characteristic is represented by the posterior distribution and the high density interval will be used. A percentage of 89% for the HDI will be used because it was shown to be more stable than the 95% HDI. A specific significance level as in the frequentist approach is not used, although the % ROPE is related to a frequentists P value, and therefore a significance level.

For phase II, Bayesian power analysis will be performed to identify appropriate sample sizes. Sample sizes for each group that result in a power >80% are considered to be appropriate. Statistical power will be calculated using simulation studies. For any combination of sample sizes, the percentage of simulations where the minimum of the HDI will be >0 (therefore indicating a true effect (or difference) between the groups for a specific hypothesis) is equal to statistical power.

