Repeated measures analysis has the advantage of increased power vis-à-vis group allocations and reduction in error variance associated with individual difference, as each subject acts as its own control. This is important for studying amputees as the group is a small proportion of the total population, and with specific inclusion/exclusion criteria the total eligible population becomes very small, making it difficult to find and recruit subjects to attain an acceptable level of power. This limited population pool often results in slightly heterogeneous sample, as the amputees available are few and far between, in every sense. Furthermore, no single amputation procedure and therefore amputated stump is exactly the same, making the experience of each amputee a bit unique. The within-subject design significantly reduces the individual differences when comparing the two conditions.

The drawback of the design is the potential of “carryover effects”, i.e. experience from one condition can affect outcome or performance in the other condition, creating a confounding extraneous variable that varies with the independent variable. Such effects are: practice, positive carryover effect to the latter condition; and fatigue, negative carryover effect to the latter condition.

● Sample size calculation

[REDACTED]

Total sample size = 14
Actual power = 0.9600638

It is therefore expected that **14** subjects are required to complete the protocol with a power of **0,95** and significance at **0,05**. Effect size was estimated based on previous in-house studies on the previous version of the product for the primary end-point.

Given a drop-out rate of **20%**, **17** subjects will be recruited.

For pass/fail criteria, see Table 4 **Endpoints, test methods and hypotheses**.

Phase II:

Sample size calculations for phase II will be done using data from phase I.

• Additional statistical matters

There is no criteria for early termination of the clinical investigation on statistical grounds.

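### Phase II power counts only the 89% HDI lying above 0, while Table 6 lists three acceptance conditions and the plan does not say which of them bind

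*Combined protocol and SAP*

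**What the plan says.** **Power rule.** Statistical design and procedures (Section 10.1) says that Phase II will be sized by simulation and that power is "the percentage of simulations where the minimum of the HDI will be >0". It adds: "Sample sizes for each group that result in a power >80% are considered to be appropriate".

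**Acceptance rule.** Table 6 gives each of 2A1, 2A2, 2B1 and 2B2 the same three entries in its acceptance column: 89% HDI lower limit at or above 0, pd above 97.0%, ROPE below 2.5%. No 'and' or 'or' joins them.

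**Text on which entries count.** Section 10.1 says "Acceptance criteria relate to the 89% HDI". It also lists the HDI, the ROPE percentage and pd side by side; the list ends with "the probability of direction (PD) will be used to gather evidence for or against each hypothesis".

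**Prior.** For Phase II, "These priors will be generated from the posterior distribution of the first trial".

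**Direction of the claims.** 2A2 and 2B2 claim improvement over Rheo Knee 3. 2A1 and 2B1 claim only parity or better, with the criterion worded "No worse rating compared to prescribed hydraulic MPK", yet they carry the same three numerical conditions.

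**The concern.** The simulated success event is one of the three conditions that Table 6 lists. If the other conditions are also required, a subgroup sized at the 80% floor has less than 80% probability of meeting the sponsor's own criteria, and a miss could reflect too few subjects rather than the device. If they are not required, the tables misstate the pass rule. Leaving the question open would let the rule be chosen after the results are known.

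A second problem sits underneath. For 2A1 and 2B1, all the listed conditions ask for evidence that the difference is positive. A subgroup sized on them is sized for a claim other than the one the hypothesis states.

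**Working it through.** **Inputs from the plan:** HDI level 89%, pd threshold 97%, power floor 80%. Phase II has no stated sample size, effect, SD or prior weight, so there is no Phase II power figure to reproduce. The check starts from exactly 80% on the plan's count and adds the pd condition.

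**Step 1: put both conditions on one scale.** For a near-symmetric posterior, an 89% HDI above 0 leaves at most 5.5% below 0, so pd > 94.5%.
- z(0.945) = 1.598 and z(0.97) = 1.881; gap g = 0.283.
- pd > 97% implies the HDI condition, so if both bind, pd decides.

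**Step 2: flat prior, fixed true effect.** z(0.80) = 0.842.
- Normal: Φ(0.842 − 0.283) = Φ(0.559) = 71.2%.
- t posterior for paired differences (noncentral t, effect solved for 80% on the HDI): 68.7%, 69.5%, 70.1%, 70.5% and 70.8% at n = 10, 14, 20, 30 and 50.
- Starting from 95% instead: Φ(1.645 − 0.283) = 91%.

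**Step 3: other priors and effect assumptions.** Let f be the share of total information held by the Phase II data (assumed 1/3, 1/2 or 0.8), and r the ratio of Phase II to Phase I information.

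| Setting | Formula | HDI plus pd |
|---|---|---|
| Phase I prior, fixed effect | Φ(0.842 − g/√f) | 64%, 67%, 70% at f = 1/3, 1/2, 0.8 |
| Flat prior, effect averaged over the Phase I posterior | Φ(0.842 − g/√(1+r)) | 73%, 74% at r = 0.5, 1 |
| Phase I prior, effect averaged over the same posterior | Φ(0.842 − g/√(f/(1−f))) | 67%, 71%, 76% at f = 1/3, 1/2, 0.8 |

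These are not bounds. With a heavier prior (f = 1/4) and fixed effect the figure is 60.9%. With a very light prior and averaged effect it approaches 80%.

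**Step 4: ROPE.** A further condition can only leave power unchanged or lower it. The limits are not in the available text, so the plan's own figure cannot be computed. Purely as illustration, assumed limits of ±0.1 SD of the differences, taken over the full posterior (flat prior, normal), give about 57%, 53% and 48% with all three conditions at n = 14, 20 and 30.

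**Step 5: sample size to restore 80% on HDI plus pd.**
- Normal: ((1.881 + 0.842)/(1.598 + 0.842))² = 1.245.
- t posterior: n = 10, 20, 30 becomes 13, 26, 38.
- Both assume a flat prior and fixed effect.

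**Step 6: pass rate for 2A1 and 2B1 when the device exactly equals hydraulic MPKs.**
- Flat prior: 5.5% on the HDI, 3.0% on pd, whatever the n.
- Informative prior with equal Phase I and Phase II information (assumption), Phase I posterior mean k posterior SDs above 0: the HDI condition passes with probability 1 − Φ(1.598·√2 − k) = 1 − Φ(2.260 − k), which is about 1%, 10% and 25% for k = 0, 1 and 1.6. This rate also changes with n.

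**The case against.** The best defence is that Section 10.1 is consistent on an HDI-only reading. It ties acceptance to the HDI, explains what an HDI excluding 0 means, and counts power on that event; pd and ROPE are described as evidence. On that reading the power definition is right and the loss is zero. This stands as a possible reading. It does not settle the matter, because Table 6 puts all three conditions in its acceptance column without ranking them.

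Four stronger readings are tempting, and the documents do not support them:

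- **That Section 10.2 proves all three conditions bind.** The sentence "For pass/fail criteria, see Table 4" sits in the Phase I text, before the Phase II subheading, and its table number points to the claims table. Its natural target is Table 5, so it is weak evidence for Phase II.
- **That 64-76% is the power when every listed condition applies.** It covers HDI plus pd only, under assumed information shares.
- **That an equal device passes 2A1 or 2B1 5.5% of the time at any n.** This holds for a flat prior, whereas the plan specifies an informative one.
- **That Phase II is underpowered.** It has no size yet, may not take place, and its rule is above 80%, not exactly 80%.

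The prior model is itself uncertain. Phase I compares with any passive MPK, while Phase II subgroups are specific to one technology and the Phase 2 text also plans to combine data across phases. The calculations treat the Phase I posterior as a prior for the same effect.

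**Conclusion.** The mismatch between the power count and the listed acceptance conditions is real, and the text leaves open which conditions bind. Its size depends on that answer:

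- **HDI only:** no power loss; Tables 5 and 6 should label pd and ROPE as supporting evidence.
- **HDI and pd:** 80% becomes about 69-71% (flat prior, fixed effect, n = 10-50). Across the priors and effect assumptions tried it is about 64-76%, which is illustrative and assumes that Phase II holds 1/3 to 0.8 of the information. Designs well above the floor lose less.
- **ROPE as well:** the same or lower, not computable from the available text.

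All figures assume a near-symmetric posterior. Under every reading, the 2A1 and 2B1 criteria do not match their hypotheses. Once those rows are reconciled, the power figures describe 2A2 and 2B2, and apply to 2A1 and 2B1 only if their criteria stay unchanged. This should be fixed before Phase II is sized.

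**What to change.** 1. Before sizing Phase II, reconcile the 2A1 and 2B1 criteria with their no-worse hypotheses.
2. In Section 10.1 and Tables 5 and 6, state which conditions must all be met and which are supporting. If ROPE binds, give its limits for each endpoint or cite where they are fixed. Correct the table reference in Section 10.2.
3. Replace the power sentence with: *Power is the percentage of simulations, under the planned prior, in which every binding acceptance condition for that hypothesis is met.* Report the achieved power on that rule if more than 80% cannot be reached.

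**Cost.** This is wording plus a changed success count in simulations not yet run. If pd binds, reaching 80% takes about 25-30% more subjects than the HDI-only floor (flat prior, fixed effect; other priors differ), and possibly more if ROPE binds. In so small a population that may be out of reach, and the lower power would then be stated. Keeping only the HDI avoids this, at the price of a 5.5% rather than 3.0% pass rate at zero true difference (flat prior, before ROPE).

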The following clinical claims/MNBA items as defined in the Clinical evaluation plan [3] are to be evaluated:

[REDACTED]	[REDACTED]

**Hydraulic MPK

No risks or anticipated adverse device effects (ADE) are to be assessed.

The hypothesis and endpoints are specified in Table 5.

For all hypothesis:

μ_1 is average of measurements at baseline (comparator);

μ_2 is the average of measurements at 3 week follow up (investigational device);

μ_3 is the average of measurements at 4 week follow up (comparator);

Phase I – Pre-launch

Data collected at phase I may be used to inform sample size needed for phase II if needed, as researchers will be using the same procedures as in phase I.

Table 5 Phase I Endpoints, test methods and hypotheses

	Hypothesis	Test Methods	Endpoints	Acceptance Criteria
1A1	Users rate their satisfaction in stair descent on the Rheo knee 4/Navii as no worse compared their prescribed MPK	
Self report: Modified PEQ ambulation subscale (item 13D)
 
Please rate how you felt about being able to walk down stairs when using your prosthesis/the test prosthesis?
 
1=cannot, 10=No problem
	Rating (1-10)	No worse rating compared to prescribed MPK $(89\% HDI_{low} \geq 0$ $pd > 97,0\%$ $ROPE < 2,5\%)$
1A2	Users rate their satisfaction in hill descent on the Rheo knee 4/Navii as no worse compared their prescribed MPK	
Self-Report: Modified PEQ ambulation subscale (item 14F)
 
Please rate your ability to walk down a steep hill when using your prosthesis/the test prosthesis?
 
1=cannot, 10=No problem
	Rating (1-10)	No worse rating compared to prescribed MPK $89\% HDI_{low} \geq 0$ $pd > 97,0\%$ $ROPE < 2,5\%)$
1B	Users balance confidence on the Rheo knee 4/Navii is no worse than on their prescribed MPK	
Self-Report (ABC Balance confidence scale)
 
Support question:
	ABC score (0-100%)	No worse ABC score than on prescribed MPK $89\% HDI_{low} \geq 0$ $pd > 97,0\%$ $ROPE < 2,5\%)$

		
Modified PEQ Satisfaction Question (16A)
 
Please rate how safe you have felt with your prosthesis/the test prosthesis? (1=extremely unsafe, 10=extremely safe)
		

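### The power and significance level that justify 14 completers belong to a test the plan does not run, so section 10.2 does not establish the operating characteristics of the Phase I acceptance rule

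*Combined protocol and SAP*

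**What the plan says.** Section 10.2 (Sample size calculation) gives software output for Phase I, "Total sample size = 14" and "Actual power = 0.9600638", and concludes that 14 "subjects are required to complete the protocol with a power of 0,95 and significance at 0,05". On the input it says: "Effect size was estimated based on previous in-house studies on the previous version of the product for the primary end-point". The input block itself is redacted.

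Section 10.1 (Statistical design and procedures) describes a Bayesian regression and states: "A specific significance level as in the frequentist approach is not used, although the % ROPE is related to a frequentists P value". It then extends that link to a significance level. On the interval it says: "A percentage of 89% for the HDI will be used because it was shown to be more stable than the 95% HDI". It also reads an 89% HDI that excludes 0 as showing a true difference.

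Table 5 sets the acceptance rule. For the primary endpoint, stair descent (1A1), the criterion is worded "No worse rating compared to prescribed MPK", followed by 89% HDI low ≥ 0, pd > 97.0% and ROPE < 2.5%. The same three thresholds apply to 1A2, 1B and 1C.

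For Phase II, section 10.1 plans power by simulation, counted as the share of runs in which the lower HDI limit exceeds 0. The readable text has nothing equivalent for Phase I.

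**The concern.** A power figure describes one decision rule at one effect size. Here the figure comes from a test at level 0.05, while success is declared on posterior criteria that involve no such test. The two could happen to agree, but nothing in the plan shows that they do.

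The 0.95 and 0.05 figures are the only readable justification for n = 14. A reader would take them to mean that, at the planned effect, the device fails the Phase I criteria about 4 to 5% of the time. If the rule is stricter than the sizing test, that failure rate is higher. How much higher depends on the prior and the ROPE limits, which the readable plan leaves open. If they are chosen at analysis, pass or fail could turn on that choice.

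**Working it through.** **Inputs.** From section 10.2: n = 14, target power 0.95, achieved power 0.9600638, significance 0.05. From Table 5: the three thresholds. Not available: effect size and test (redacted), sidedness, Phase I prior, ROPE limits, and whether all three criteria must hold. Assumed: sizing by paired t-test, normally distributed differences, a flat prior, all three criteria required. ROPE half-width is varied in units of the SD of the within-subject difference.

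**Step 1: the plan's own figure.** It cannot be reproduced directly without the effect size, so I solved for the effect that gives it. Power = P(T > c), where T is noncentral t with 13 df and noncentrality dz·√14.
- Two-sided 0.05: c = 2.160, and power 0.9600638 gives dz = 1.075.
- One-sided 0.05: c = 1.771, and the same power gives dz = 0.960.
- At n = 13 these effects give 0.944 and 0.947, both below 0.95. So 14 is the smallest n for the target either way, and the printed output is consistent with a paired t-test.

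**Step 2: the thresholds on the t scale.** With a flat prior the posterior of the mean difference is t with 13 df around the observed mean.
- 89% HDI low ≥ 0 leaves (1 − 0.89)/2 = 0.055 in the lower tail, so t ≥ 1.715. That is one-sided 0.055, or two-sided 0.11.
- pd > 97% leaves 0.03, so t > 2.060. That is one-sided 0.03, or two-sided 0.06.
- Since 2.060 exceeds 1.715, the pd criterion implies the HDI criterion. Before ROPE is considered, the rule is a one-sided test at 0.03.

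**Step 3: pass probability at n = 14.** The first two rows are from the noncentral t. The ROPE rows are simulated, with the ROPE fixed on the true SD scale and its share taken over the full posterior.

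| Rule | Zero difference | dz = 0.960 (one-sided sizing) | dz = 1.075 (two-sided sizing) |
|---|---|---|---|
| HDI only | 0.055 | 0.965 | 0.987 |
| HDI and pd | 0.030 | 0.927 | 0.968 |
| All three, ROPE ±0.05 SD | 0.028 | 0.927 | 0.968 |
| All three, ROPE ±0.07 SD | 0.02 | 0.918 | 0.964 |
| All three, ROPE ±0.1 SD | 0.013 | 0.88 | 0.95 |
| All three, ROPE ±0.2 SD | 0.004 | 0.76 | 0.87 |
| All three, ROPE ±0.3 SD | 0.001 | 0.63 | 0.77 |

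Scaling the ROPE to the sample SD moves these slightly; at ±0.1 SD, power is 0.874 and 0.937. Taking the ROPE share inside the 89% HDI is more lenient: at ±0.3 SD, with the sample SD, power is 0.815 and 0.900.

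**Step 4: the link from % ROPE to a P value.** Data at exactly two-sided p = 0.05 with n = 14 (t = 2.160) put 3.6%, 8.5% or 39% of the posterior inside a ROPE of ±0.1, ±0.2 or ±0.5 SD. One P value thus maps to very different ROPE shares. Until the ROPE limits are stated, the link gives no significance level.

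**The case against.** The strongest reply is that agreement is possible. With two-sided sizing and a ROPE near ±0.07 SD, the same flat-prior model gives power of about 0.964 and a one-sided error of about 0.02, close to 0.96 and to two-sided 0.05. Section 10.1 also ties acceptance to the 89% HDI, and on the HDI alone power is 0.965 or 0.987, above the printed figure. The lower values come from ROPE widths that I assumed. All of this stands. A reader might infer that the rule has neither the stated power nor the stated error rate. The documents do not support that, because the effect, test and sidedness cannot be read and the prior and ROPE limits are not given.

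A reader might also infer that devices with no difference would be accepted 11% of the time. That is not so. The 0.11 is a two-sided figure for the 89% HDI alone, and it bears only on the section 10.1 sentence about a true difference. The full Table 5 rule looks in one direction and passes at most about 3% of the time at zero difference.

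Finally, the plan says only that % ROPE is related to a P value, not that the relation is fixed. For a given n and ROPE the two are indeed linked. What remains is that no ROPE is given, so the sentence cannot connect the analysis to the 0.05 used for sizing.

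The reply does not remove the gap. The HDI-only reading disregards two of the three criteria printed in Table 5, and agreement under one chosen ROPE width is not something the plan states or shows.

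**Conclusion.** The point holds in this form: the power and level in section 10.2 belong to a test that is not run, so they do not establish the power or the false-acceptance rate of the Phase I rule. Under the stated assumptions, power at the implied effect lies between about 0.97 and about 0.63. Failure at the planned effect would then be about 3% to 37%, against the 4% implied by 0.96. False acceptance at zero difference is at most about 0.03. Separately, reading an 89% HDI that excludes 0 as a true difference corresponds to about 0.11 two-sided under a flat prior.

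The range reflects what the plan leaves open; it is not an estimate of the trial's actual power. The printed 0.9600638 is not shown to be wrong for the test it describes, and the redaction of its inputs is not a fault. An informative prior would change all of these figures.

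**What to change.** In section 10.1, state the Phase I prior, the ROPE limits on each endpoint's scale, whether the ROPE share is taken over the full posterior or inside the HDI, and how the three Table 5 criteria combine.

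In section 10.2, replace the power of 0.95 (0.96 achieved) at significance 0.05 with the simulated probability of meeting the Table 5 rule at n = 14, once at the assumed effect and once at zero difference. Section 10.1 already plans HDI-based simulation for Phase II; the Phase I version should use the full rule.

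Replace the sentence linking % ROPE to a P value and a significance level with one saying that, under a flat prior, pd > 97% corresponds to about one-sided 0.03.

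The cost is one short simulation and a few lines of text. The stated power may become less favourable; n stays at 14 and the figure attached to it is corrected.
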